4.0 Study Design

4.1 *Describe and explain the study design (e.g. case-control, cross-sectional, ethnographic, experimental, interventional, longitudinal, observational).*

Response: This Veggie Van effectiveness and implementation study, funded by the NIH, will be overseen by Drs. [name], [name], Co-Investigator, [name], Co-Investigator, and [name], Co-Investigator. This study will be coordinated by project coordinators and staff at UB and UNC.

For Aim 2 of the study, all study related procedures will be carried out by UB staff.

Aim 2: After 9 qualified organizations* have been identified among applicants, we will randomize proposed MM sites (33 total across all partner organizations), to an intervention (MM program implementation) or comparison condition (extended planning). Randomization will be stratified within each organization so that each organization will have 2 intervention and 2 comparison sites. One organization will have 5 sites. The 5th site will allow for more thorough testing of protocol procedures. This ensures that study groups will be balanced at the organizational level. The condition for which each proposed MM location was selected will be communicated at the time of award. Organizations will communicate to intervention sites that they want to open a MM at that location within the next year. Organizations will communicate to comparison sites that they want to work with them on a food systems planning process to determine if a MM program is the right fit for their location. At the end of the year-long planning process with comparison sites, the organization and proposed MM site will decide together how to proceed (start a MM, apply for grant funding for a different project; etc.).

Both arms will undergo community engagement efforts that serve to both identify potential research participants and engage them in the planning for a MM. Intervention sites will work with a community advisory committee to develop an engagement plan to raise community awareness of the forthcoming MM. Comparison sites will work with a community advisory committee to engage community members in a food access planning process.

Both intervention and comparison sites will distribute sign-up forms as part of the community engagement process. UB staff will identify from the sign-up forms those interested in participating in the study. Consent will be obtained via phone. Phone surveys and in-person data collection will then be completed.

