[figure not shown]
Statistical Analysis Plan (SAP)

Effectiveness and Implementation of a Research Tested Mobile Produce Market Designed to Improve Diet in Underserved Communities

Principal Investigator	[name] Associate [name] of Community Health and Health Behavior School of Public Health University at Buffalo Buffalo, NY
Protocol identification number	1144594
ClinicalTrials.gov identifier	NCT04246593
Author	[name], PhD Assistant Director of Research and Evaluation Community Health Interventions Lab Department of Community Health and Health Behavior School of Public Health University at Buffalo Buffalo, NY
Version	1
Date	2/3/2025

SIGNATURE PAGE

Principal Investigator

[name]

Author

[name]

ABBREVIATIONS

BMI	Body Mass Index
F&V	Fruits and Vegetables
MM	Mobile Market
RFP	Request for Partners
SAP	Statistical Analysis Plan
SNAP	Supplemental Nutrition Assistance Program
TANF	Temporary Assistance for Needy Families
VV	Veggie Van
WIC	Special Supplemental Nutrition Program for Women, Infants, and Children

TABLE OF CONTENTS

1. Introduction.....	5
2. Study design.....	5
2.1 Sample size calculation.....	7
3. Aims and objectives	8
4. Outcomes	8
4.1 Primary Outcome	8
4.2 Secondary Outcomes.....	9
4.3 Other Outcomes.....	9
5. Population to be Analyzed	9
6. Analyses.....	9

1. Introduction

The goal of the Veggie Van (VV) study is to evaluate the effectiveness of mobile produce markets using the VV mobile market (MM) model through a 12-month cluster-randomized controlled trial in 33 communities.

This statistical analysis plan (SAP) will describe the endpoints of the study and the analyses to evaluate our main outcomes.

2. Study design

We utilized a request-for-partners (RFP) process to recruit organizations as study partners; nine organizations were selected as partners and asked to implement the Veggie Van model at new mobile market sites and facilitate recruitment of mobile market customers for the study and data collection activities. Each study partner organization was asked to partner with four community sites that serve as potential locations for the mobile market program, known as community sites.

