Partner organizations will choose two sites they would start working with first based on timeline and readiness. These two sites will be paired for the purposes of randomization; one will be randomized to the mobile market site (intervention) and the other to the planning site (control). The same process will be used for the remaining pairs of sites as applicable. Partner organizations will run a mobile market following the Veggie Van model for at least one year at community sites randomized to the mobile market intervention. Planning sites partake in a year-long food access planning process to help determine if the surrounding community would benefit from a mobile market at that location. After one year, the partner and the planning site can decide to implement a mobile market, or another food access program based on community feedback gathered through the planning activities. Two months prior to the launch date of both the mobile market site and the planning site activities, partner organizations work jointly with community sites to engage the community to raise awareness of the mobile market and to recruit potential customers to participate in the Veggie Van Study.

Partner organizations will identify individuals who are interested in learning more about a mobile market in their community. To facilitate recruitment to the Veggie Van study, the partner and community site will utilize interest forms or sign-up sheets to collect community member contact information. If community members indicate interest in participating in the Veggie Van Study, the research team will contact them to screen, provide consent, and enroll into the study.

[figure not shown]
The goal is to recruit at least 30 participants at each of 32 proposed mobile market sites (960 total). Eligible individuals include those at least 18 years old, ability to speak English and/or Spanish, are the primary grocery shopper for their household, and live near or otherwise regularly frequent the community site. A threshold was established to ensure that market sites will be serving a predominantly lower-income community and that the study team is sampling from the appropriate target population. At least 60% of eligible sign-up forms are required to be from individuals that self-identify as receiving government assistance such as: the Supplemental Nutrition Assistance Program (SNAP), the Special Supplemental Nutrition Program for Women,

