2.1 Sample size calculation

Our primary outcome is change in F&V intake (cups/day) at 12 months using the 24-hour recall, thus, we will compare the difference in mean changes in F&V between intervention and comparison group participants. In the sample size and power analyses, we considered similarity in changes in F&V among participants within a site (intra-class correlation, ICC), and the fact that the intervention is at the site level (54, 55). Based on a previous cluster RCT, we estimated the ICC for change in F&V intake to be 0.08 (SD 2.7); We expect the MM program to increase the F&V intake by at least 1 cup/day (effect size of approximately 0.4). Using one-sided tests of

significance at $p=0.05$, an $ICC = 0.08$, and cluster size = 21 participants per site, 12 sites per group will provide at least 80% power to detect the anticipated change in F&V consumption. To account for possible attrition or extended delays on the part of the organization, we will over-recruit (i.e., select more organizations than needed as part of the RFP process). While we need 6 organizations (24 MM sites) to achieve the desired power (Table 4), we will recruit 8 organizations (32 sites). We expect participant attrition to be no more than 30% based on previous work, so we will plan to recruit about 30 participants per site.

Table 1: Power Calculation

Actual Power ($1-\beta$)	Difference in Mean Change in F&V	No. of Sites Per Study Group	No. of Participants per Site	Sample Size Per Study Group	Sample Size Per Group with 30%
0.80	1.0	12	21	252	328
0.81	1.0	16	11	176	229
0.80	1.0	20	8	160	200
0.80	.75	20	45	900	1285

3. Aims and objectives

To measure MM effectiveness at sites randomized to implement a MM for 1 year versus a planning (control) condition. Measure MM effectiveness at improving the following outcomes between baseline and 1-year follow-up: 1.) self-reported diet measured via two 24-hour dietary recalls, 2.) BMI based on in-person height and weight measurements; 3.) an objective indicator of F&V consumption (dermal carotenoids measured via finger scan) and 4.) Social Cognitive Theory diet-related constructs including self-efficacy and food environment.

4. Outcomes

This section will present outcomes investigated in the RCT to answer the above study aims and objectives.

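### Sites are randomised in pairs within partner organisation, but the primary model has only a site random intercept; if organisations differ in mean change, its interval is wider than the design supports

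*SAP*

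**What the plan says.** **Allocation.** Protocol 4.1: "Randomization will be stratified within each organization so that each organization will have 2 intervention and 2 comparison sites". It gives the purpose: "This ensures that study groups will be balanced at the organizational level". SAP section 2 describes the mechanism: "Partner organizations will choose two sites they would start working with first based on timeline and readiness". It continues: "These two sites will be paired for the purposes of randomization; one will be randomized to the mobile market site (intervention"), and the remaining sites are handled the same way.

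**Primary model.** Protocol 17.1 specifies a mixed model for change in intake with the baseline value and intervention as fixed effects and a random intercept for site. SAP section 6 names a mixed model with a random intercept for clustering within sites, then further models adjusting for baseline intake, race and income. No organisation or pair term appears in either.

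**Elsewhere.** Protocol 17.1 mentions organisation only as a possible moderator in expanded, exploratory models. SAP section 6 says the secondary-outcome models control for baseline covariates and site clustering. It does not list the covariates and names no stratum.

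**Counts.** Protocol 4.1 has nine organisations and says "we will randomize proposed MM sites (33 total across all partner organizations"). It adds: "One organization will have 5 sites". SAP section 2 also has nine organisations: "Each study partner organization was asked to partner with four community sites". SAP 2.1 says "we will recruit 8 organizations (32 sites").

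**The concern.** Each organisation contributes sites to both arms. Any shift in mean change shared by all of an organisation's sites therefore cancels from the difference between arms. A model with only a site random intercept does not know this. It counts the shared shift as site-to-site noise and carries it into the standard error of the intervention effect.

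The estimate itself is not affected. What is at stake is precision: the design pays for within-organisation balance and the planned analysis does not use it. The loss could be nil or appreciable, depending on how much of the between-site variance lies between organisations.

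**Working it through.** **Inputs from SAP 2.1:** SD of change 2.7 (variance 7.29), ICC 0.08, 21 completers per site, difference 1.0 cup/day, one-sided 0.05, 12 sites per arm for the power statement, and 32 sites (16 per arm, 8 organisations) as the planned layout.

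**Assumed:** the share *s* of the ICC variance that lies between organisations, taken as 0, 10, 25 and 50%. Site sizes are equal, with 2 + 2 sites per organisation.

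**Step 1. The plan's own figure.** Design effect 1 + 20 × 0.08 = 2.6. Effective size per arm 252 / 2.6 = 96.9. SE = 2.7 × √(2/96.9) = 0.388. Power from a noncentral t with 22 df is 0.803, which matches the SAP's 0.80. (Protocol 17.2 states at least 90% from the same inputs. That does not reproduce, and is a separate matter.)

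**Step 2. True SE under the actual allocation.** With organisation balanced across arms, its variance drops out. For *k* sites per arm:

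SE = √{2 × 7.29 × [0.08(1 − s) + 0.92/21] / k}

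With k = 16: 0.336, 0.325, 0.308 and 0.276 for s = 0, 10, 25 and 50%.

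**Step 3. SE that the site-only model reports.** It pools the variance of site means within arm. With 16 sites per arm in 8 organisations of two, that pool retains (16 − 2)/15 = 14/15 of the organisation variance. At s = 25% the expected SE is √{14.58 × [0.06 + 0.0438 + 0.02 × 14/15] / 16} = 0.334, against a true 0.308. That is too large by a factor of 1.09. At 50% it is 0.332 against 0.276, a factor of 1.20.

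**Step 4. Operating characteristics.** Simulated site means, 200,000 trials per setting, t tests with 30 df (site-only) and 23 df (organisation terms), common effect, 16 sites per arm:

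| Assumed share | Type I error, site-only | Type I error, organisation | Power, site-only | Power, organisation | 95% half-width, site-only | 95% half-width, organisation |
|---|---|---|---|---|---|---|
| 0% | 5.0% | 5.0% | 0.897 | 0.893 | 0.68 | 0.69 |
| 10% | 4.4% | 4.9% | 0.903 | 0.909 | 0.68 | 0.67 |
| 25% | 3.8% | 5.0% | 0.915 | 0.934 | 0.68 | 0.63 |
| 50% | 2.6% | 5.0% | 0.937 | 0.969 | 0.67 | 0.57 |

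From unrounded half-widths, organisation terms widen the interval by about 1% at 0% (0.687 against 0.680). They narrow it by 2% at 10% (0.665 against 0.679), 7% at 25% (0.630 against 0.676) and 16% at 50% (0.566 against 0.671). With 12 sites per arm (6 organisations) and s = 25%, power is 0.825 site-only and 0.854 with organisation terms.

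**Step 5. Effects that vary by organisation.** Assume an effect variance of half the site variance (7.29 × 0.08 = 0.583) and s = 25%, with 16 sites per arm.
- Inference to these organisations: one-sided type I error is 2.9% site-only and 4.2% with organisation terms; power is 0.894 and 0.920.
- Inference to a wider population of organisations: type I error is 5.3% and about 7.0%.

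**Step 6. Cost when organisations do not differ (s = 0).** Noncentral t power for site-only, organisation and pair terms is 0.897, 0.893 and 0.884 at 16 sites per arm (30, 23 and 15 df). At 12 per arm it is 0.803, 0.796 and 0.779 (22, 17 and 11 df).

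**Step 7. Can the strata be coded?** Nine organisations with four sites and one extra site gives 9 × 4 + 1 = 37, not 33. With nine organisations, 33 sites and one organisation of five, the other eight average (33 − 5)/8 = 3.5 sites, so 2 + 2 cannot hold in all of them. The SAP's 8 × 4 = 32 is consistent in itself but conflicts with the nine organisations in its own section 2.

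**The case against.** **The benefit is assumed.** This stands. No document gives a between-organisation variance. At a 0% share the change loses a little; at 10% it gains 0.6 points of power and 2% of width. Adjustment for baseline intake, race and income may absorb part of any organisation variance. A reader might take the planned moderator analyses in protocol 17.1, or the 2020 disruption noted in SAP section 6, as evidence that organisations differ in mean change. Those passages point mainly to variation in the effect, and do not establish a shared shift in both arms.

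**The inference may be meant to reach further.** This stands in part. Protocol 3.1 speaks of testing the model across multiple organisations and refining a toolkit for future markets. If effects vary and the result is generalised, organisation fixed effects are less well calibrated than the site-only model (about 7.0% against 5.3% in the assumed case). So the remedy should not simply declare the narrower target; it should say what each interval covers.

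**The error is harmless in direction.** True under a common effect: the estimate is unbiased and the test conservative. That limits the weight of the point. It does not remove the case for analysing by the groups used to randomise.

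**The secondary models may already include organisation.** They may. SAP section 6 leaves the covariates unlisted, so a reader cannot infer that organisation is excluded, only that it is not named.

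**It is late to change a primary model.** SAP section 6 already reports analyses in the past tense with baseline p-values, so a change that may narrow the interval needs to be transparent. Dating it, basing it on the allocation scheme and showing both results answers most of this.

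**Conclusion.** The point holds as an inexpensive improvement to efficiency. The allocation is restricted within organisation and the primary model does not use that restriction. If organisations differ in mean change, and the effect is common or inference is to the participating organisations, the site-only interval is too wide. The excess runs from nothing to roughly a sixth of its width over assumed shares of 0 to 50%.

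A reader might infer that ignoring the strata invalidates the primary test or inflates false positives. The documents do not support that. Organisation is balanced by allocation whatever the model, the type I error falls below nominal under a common effect, and the SAP's 80% power reproduces without an organisation term. Nor does the mismatch in site counts support the modelling point. It is a separate inconsistency that matters here only because the strata must be known before they can be coded.

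The figures rest on equal site sizes, a balanced layout and the assumed shares.

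**What to change.** In protocol 17.1 and SAP section 6:

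1. Add organisation, the randomisation stratum, as a fixed effect beside the site random intercept in the primary and secondary models, with Kenward-Roger or Satterthwaite degrees of freedom.
2. Enter this as a dated amendment justified by the allocation scheme, and report the site-only result beside it.
3. Use a pair-level model as a sensitivity analysis only. Pairs were formed on timeline and readiness, and their terms cost more degrees of freedom.
4. State that the organisation-adjusted interval covers the average effect in the participating organisations. State also that neither it nor the site-only interval allows for variation in effect across organisations if the result is generalised as protocol 3.1 suggests.
5. Separately, reconcile the numbers of organisations and sites (9 and 33 against 8 and 32, with 37 implied by four each plus one), so that organisation, pair and arm can be coded for every randomised site.

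**Cost.** One factor per model and an amendment; no new data. If organisations do not differ, organisation terms lose about 0.4 points of power at 16 sites per arm and 0.7 at 12. Pair terms would lose about 1.3 (0.897 − 0.884) and 2.4 (0.803 − 0.779). If effects vary and inference is to wider organisations, the organisation-adjusted test is the less well calibrated of the two, which is why item 4 is needed.

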2.1 Sample size calculation

Our primary outcome is change in F&V intake (cups/day) at 12 months using the 24-hour recall, thus, we will compare the difference in mean changes in F&V between intervention and comparison group participants. In the sample size and power analyses, we considered similarity in changes in F&V among participants within a site (intra-class correlation, ICC), and the fact that the intervention is at the site level (54, 55). Based on a previous cluster RCT, we estimated the ICC for change in F&V intake to be 0.08 (SD 2.7); We expect the MM program to increase the F&V intake by at least 1 cup/day (effect size of approximately 0.4). Using one-sided tests of

significance at $p=0.05$, an $ICC = 0.08$, and cluster size = 21 participants per site, 12 sites per group will provide at least 80% power to detect the anticipated change in F&V consumption. To account for possible attrition or extended delays on the part of the organization, we will over-recruit (i.e., select more organizations than needed as part of the RFP process). While we need 6 organizations (24 MM sites) to achieve the desired power (Table 4), we will recruit 8 organizations (32 sites). We expect participant attrition to be no more than 30% based on previous work, so we will plan to recruit about 30 participants per site.

Table 1: Power Calculation

Actual Power ($1-\beta$)	Difference in Mean Change in F&V	No. of Sites Per Study Group	No. of Participants per Site	Sample Size Per Study Group	Sample Size Per Group with 30%
0.80	1.0	12	21	252	328
0.81	1.0	16	11	176	229
0.80	1.0	20	8	160	200
0.80	.75	20	45	900	1285

3. Aims and objectives

To measure MM effectiveness at sites randomized to implement a MM for 1 year versus a planning (control) condition. Measure MM effectiveness at improving the following outcomes between baseline and 1-year follow-up: 1.) self-reported diet measured via two 24-hour dietary recalls, 2.) BMI based on in-person height and weight measurements; 3.) an objective indicator of F&V consumption (dermal carotenoids measured via finger scan) and 4.) Social Cognitive Theory diet-related constructs including self-efficacy and food environment.

4. Outcomes

This section will present outcomes investigated in the RCT to answer the above study aims and objectives.

4.1 Primary Outcome

Consumption of fruits and vegetables (F&V) will be measured at baseline and 12 months. Change in F&V intake (cups/day) at 12 months will be calculated from four 24-hour recalls (2 at baseline and 2 at 12-months) which will be administered over the phone by trained interviewers (in English or Spanish). One recall at each time point will be from a weekday and the other from a weekend day. The 24-hour dietary recalls will be collected using the Nutrition Data Systems for Research (NDSR) computer-based software application developed at the University of Minnesota Nutrition Coordinating Center (NCC); NDSR uses a five pass interview approach with interview prompts in English and Spanish (49). The NCC Food and Nutrient Database serves as the source of food composition information in NDSR (50). When a participant completes their in-person data collection, participants will receive The Food Amounts Booklet to have as a visual reference during the 24-hour recall. This booklet is compatible with the NDSR program.

4.2 Secondary Outcomes

Body Mass Index (BMI)

BMI will be calculated at baseline and 12 months from weight measured using a Seca 876 digital scale (maximum capacity of 250 kg) and height measured to the nearest 1/8 inch using a Seca stadiometer. Weight and height will be combined to report BMI in kg/m².

Dermal Carotenoids

Dermal Carotenoids will be measured at baseline and 12 months using a finger scan technology called the “Veggie Meter” which relies on pressure mediated Raman Spectroscopy (RS) and is thought to be a valid indicator of changes in skin carotenoids in response to dietary carotenoid consumption.

4.3 Other Outcomes

Psychosocial measures – Self-efficacy

Self-efficacy to purchase, prepare and eat fresh F&V and will be measured with a 10-point Likert scale using a selection of items adapted from a study of shoppers where self-efficacy was shown to be correlated with nutrition behaviors and will serve as a comprehensive assessment of the effect of the educational intervention.

Psychosocial measures - Benefits (expectations)

Benefits (expectations) and barriers to eating F&V will be measured using a 4-point Likert scale (strongly agree, agree, disagree, strongly disagree) previously tested in lower-income adults which reflects common benefits/barriers found in the literature.

Psychosocial measures will be measured at baseline and 12 months.

5. Population to be Analyzed

To be eligible for the study, individuals had to be at least 18 years old, able to speak English and/or Spanish, be the primary grocery shopper for their household, and live near or otherwise regularly frequent the site. Individuals were ineligible if they were planning to leave the area or stop frequenting the site within the next year. To ensure that sites were predominantly serving lower-income community members and that the study team was sampling from the appropriate target population, a goal was set that at least 60% of eligible sign-ups are from individuals who self-report utilizing assistance programs (e.g., SNAP, WIC, TANF, Medicaid, Work First, and/or housing assistance).

6. Analyses

In order to test the impact of the VV intervention on change in F&V intake, we used generalized linear mixed model (GLMM) with random intercept to control for clustering within sites. In order to further explore the intervention effect, we fit GLMMs that adjust for (1) baseline dietary intake and (2) race and baseline income due to significant differences between groups at baseline

(race $p=.01$; income: $p=0.02$). Including the baseline values as a covariate in an analysis of covariance (ANCOVA) is known to be a more powerful test than a group comparison of baseline to post-intervention change (42, 43). ANCOVA is not distorted by regression towards the mean bias, whereas a change analysis is subject to that bias (42, 43). We also conducted a sensitivity analysis excluding extreme F&V reporters, defined as participants who had a change (increase or decrease) greater than 10 servings of F&V per day based on generating histograms and identifying outliers in the data distribution. We conducted additional analyses comparing change in F&V intake for those who reported ever purchasing from VV (VV users) to those who did not report shopping at VV (VV non-users), including delayed-intervention control participants. Due to major disruptions to VV operations in the beginning of the study period (2020), we also looked for differences among a sub-sample of sites that launched after the peak of COVID-19 related closures defined as launching in 2021 or later (i.e., post-covid sites). All secondary outcome analyses were conducted using GLMMs and controlled for baseline covariates of interest and clustering within sites.

Additional analyses by question set can be found below:

Question Set	Answer options	Variable Creation	Analysis Plan
Demographics (13) Weight is asked again at follow-up	various	Will combine categories with small numbers of respondents BMI: created from height and weight	
For all main outcomes we need to control for site and relevant demographic variables
 
 1. Descriptive 2. Will test for differences between Ix and Control groups and include any variables that differ as co-variates in outcome analyses 3. BMI is Aim 1 outcome- compare intervention and control at 6 and 12 months. We expect BMI to stay the same for intervention at 6 months and decrease at 12 months whereas control will increase over time.

NCI F&V Screener (11)*	Frequency (per day, week or month) plus Portion Size	See below for scoring	Aim 1 Outcome. We hypothesize an increase in F&V consumption for intervention compared to control at 6 months.
F&V 2-question*	Servings per day	Continuous	Aim 1 Outcome. We hypothesize an increase in F&V consumption for intervention compared to control at 6 months and that differences will be maintained at 12 months. We want to compare the 2 F&V measures and possibly combine them as was done in NC Strides and other projects
NHANES FFQ-Sweets (7)*	Frequency (per day, week or month)	1. Convert all answers to per day or per week depending on which seems more reasonable. 1 month=4.348 weeks 1 week=7 days 2. Sum all 7 questions to get a combine servings per (week or day) score	Aim 1 Outcome. We hypothesize a decrease in sweet consumption for intervention compared to control at 6 months.
Barriers to F&V (12)*	Strongly agree (1) Agree (2) Disagree (3) Strongly disagree (4) Don't know (5)	Answers 5, 6 and 7 will be treated as missing If answers are normally distributed, we will combine 1&2 and 3&4 and create a dichotomous variable. If answers are weight to one end or the other,	Descriptive Correlate with F&V consumption at each timepoint Mediator of F&V consumption

	Skip refuse (6) N/A (7)	we will look at them as 4-category variables or combine categories as is appropriate	
Shopping Behavior (10)* 2 questions repeated at follow-up	Various	
Will combine categories with small numbers of respondents (q65)
 
 - mark 6 and 7- skip/refuse as missing for baseline and follow-up - for everyone else, subtract follow-up from baseline - If number is positive then re-categorize as 1= shopping more often - If number is negative then re-categorize as 2= shopping less often - if number is 0, re-categorize as 3= shopping the same frequency 	
Descriptive at baseline
 
For questions available at follow-up:
 
(q65) Percent of people who shop more often, less often or the same at each type of store
 
 - Compare intervention vs. control percentages 
(q66 follow-up) calculate percent of people who answer “Veggie Van” as one of the stores they most shop at- compare intervention vs. control percentages

Importance to buy/make/eat F&V (1)*	5- point likert scale	If answer= 6 (don't know) or 7 (skip/ refuse), categorize as missing and treat remaining as continuous variable	
Descriptive
 
Correlate with F&V consumption at each timepoint
 
Mediator of F&V consumption

Cooking at home (1)*	Days per week	
Create a continuous variable
 
If they choose 1 then the number they enter is the days per week
	
For baseline, we will just look at descriptive – i.e. days per week cooking at home
 
For follow-up we will look at the percent of people who

		
If they chose 2 (never) then enter as 0 days per week
 
If they choose 3 or 4 (don't know or skip/refuse) then treat as missing
 
 - for everyone else, subtract baseline from follow-up - If number is positive then re-categorize as 1= cooking more often - If number is negative then re-categorize as 2= cooking less often - if number is 0, re-categorize as 3= cooking the same frequency 	
cook more often, less often or the same at each type of store at follow-up
 
 - Compare intervention vs. control percentages (chi-sq??)
Self- Efficacy Cooking F&V (7)*	5- point likert scale	
If answer= 6 (don't know) or 7 (skip/ refuse), categorize as missing and treat remaining as continuous variable
 
Need to complete factor analysis with pilot data to see if questions should be used as a scale or individual
	
Aim 1 Outcome. We hypothesize an increase in self-efficacy for intervention compared to control at 6 months
 
Additional analyses:
 
 - Correlation between F&V consumption and self-efficacy at baseline - Correlation between changes in F&V consumption and changes in self-efficacy at follow-up

			
 - If correlated at follow-up we will complete mediation analysis.
Self- efficacy Eating Veg (9)*	5- point likert scale	
If answer= 6 (don't know) or 7 (skip/ refuse), categorize as missing and treat remaining as continuous variable
 
Need to complete factor analysis with pilot data to see if questions should be used as a scale or individual
	
Aim 1 Outcome. We hypothesize an increase in self-efficacy for intervention compared to control at 6 months
 
Additional analyses:
 
 - Correlation between F&V consumption and self-efficacy at baseline - Correlation between changes in F&V consumption and changes in self-efficacy at follow-up - If correlated at follow-up we will complete mediation analysis.
